**Statistical Analysis Plan (SAP)**

1. Analysis of baseline parameters, including: age, sex, body weight (kilograms), nPCR, serum albumin, hemoglobin, serum phosphorus, serum calcium, intact parathyroid hormone (iPTH), KT/V, WCC, dietary protein intake(DPI), dietary energy intake(DEI) and the protein provided by the egg white.
2. Analysis of parameters after 12 months, including: body weight (kilograms), nPCR, serum albumin, hemoglobin, serum phosphorus, serum calcium, intact parathyroid hormone (iPTH), KT/V, WCC, dietary protein intake(DPI), dietary energy intake(DEI) and the protein provided by the egg white.
3. Analysis of the difference of the incidence of peritonitis, readmission and switching to hemodialysis or renal transplant and lost follow-up.

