suitable kind of protein intake) and calorie intake. And then they will be randomly assigned into one of two parallel groups: (1) Control group: Intervention with conventional education every 1-3 months during routing clinical visit ;( 2) Intervention group: wechat delivery of dietary education: Intervention with conventional education will occur every 3 months during routing clinical visit and wechat model of dietary education will occur every 1 month by cellphone. The control group will also receive monthly cell phone calls but without the wechat intervention. The wechat model will provide information on protein, calcium, phosphorus and sodium intake, suggested by the current KDIGO/ KDOQI guideline. The wechat model will include pictures, words, video and voice. Furthermore, we will emphasize the use of egg white protein which may be effective dietary component lowering serum phosphorus without risking malnutrition. The baseline characteristics included the following variables : age, sex, diabetes, cause of kidney disease if known, medication list, comorbid condition list, smoking history, body weight (kilograms), blood pressure , PCR, serum albumin, serum total protein, C-react protein(CRP)、 white blood cell count(WBC), hemoglobin, serum phosphorus, serum calcium, serum sodium, serum magnesium, serum uric acid, intact parathyroid hormone (iPTH), vitamin D, bicarbonate, KT/V, WCC. The study period will be 12 months, with the patients returning every 3 months for measurement of parameters, peritoneal equilibration test (PET), calculation of KT/V and WCC by software, dietary interviews and 3 day dietary recall and conventional education of PD. And we will record the incidence of peritonitis, readmission and switching to hemodialysis and mortality rate. During the course of study, the dose and types of medication could be changed if medically necessary in the view of the treating physician.

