#### **Efficacy Assessments (What data will be collected/utilized?):**

Wechat is available and convenient for all kinds of platforms with a little network traffic fee (less than 10 RMB per month); enjoy group chat and private chat; support voice, photo, video and text messages. Baidu search found that at present 600 million people had registered wechat in China. We will use the software of wechat to send message to our PD patients with the Nutrition knowledge of protein, phosphorus, calcium and sodium. And the messages will be picture or/and video of food model with voice or/and words notes. Egg whites are tasty and readily available with a low phosphorus content and could be a good source for additional protein intake for the PD patients. The outcomes of our study may be the following:(1) The protein intake of PD patients will achieve or be close to the target of 1.2g/kg/d in intervention with wechat group; (2) Changes in parameters of primary endpoints from baseline to last evaluation may be show significant difference between the intervention with wechat group and the control group; (3) The incidence of peritonitis, readmission, switching to hemodialysis and mortality rate may be lower in the intervention with wechat group compared with the control group. Furthermore the limitations of our study are the single center design.

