#### **Statistical Methods (for analyzing primary & secondary endpoints):**

Continuous variables are reported as mean $\pm$ SD. Categorical variables are reported as frequency and percentage. Comparisons between values of intervention with wechat group and values of controlled group at every time points of study will be made. Continuous variables with normal distribution will use analysis of t-test. Continuous variables with abnormal distribution will use analysis of rank-sum test. Categorical variables will use analysis of covariance. Regression analysis will be performed to comparing the levels of primary endpoints, with PCR being the independent variable. Logistic regression analysis will be performed within the secondary endpoints. All statistical tests were conducted at a significance level of  $\alpha = 0.05$ . All the statistical analyses will be conducted with Empower Stats.

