**Is the study sufficiently powered (adequate sample size) to answer the research question? Explain:**

We tested a sample population of 10 patients treated at the PD center who successfully completed training and were on therapy for at least 3 months. At the time of the first clinic visit, we collected data and calculated mean  $\pm$  SD of PCRs as  $0.834 \pm 0.154$  using SPSS (version1.6). According to sample size counting formula  $N = 2^*[(\alpha+\beta)^*\sigma/\delta]^2$ , we calculated that a total sample size of 50 patients in each group will be needed to detect a significant difference ( $P<0.05$ ) in PCR of  $+0.090$  g/(kg.d) from baseline to last measurement during the study between the wechat group and control group. The sample size (assuming a 20% dropout rate) was estimated at 60 patients in each group. So we think this study is sufficiently powered to answer the research question.

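### The main nPCR comparison has no single time point and no rule for patients without a 12-month value, although 20% dropout is expected

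*Combined protocol and SAP*

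**What the plan says.** The basis of the main comparison appears in four places.

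- SAP, item 2: "Analysis of parameters after 12 months", with nPCR in the list.
- Efficacy Assessments: "Changes in parameters of primary endpoints from baseline to last evaluation".
- Sample-size section (the question on whether the study is sufficiently powered): a PCR difference of +0.090 g/(kg.d) "from baseline to last measurement during the study between the wechat group and control group".
- Statistical Methods: comparisons of the two groups' values "at every time points of study will be made", by t-test or rank-sum test for continuous variables.

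The schedule under Specific details of Treatment/Intervention is fixed: "The study period will be 12 months, with the patients returning every 3 months". The sample-size section inflates its figure "assuming a 20% dropout rate". SAP item 3 compares "switching to hemodialysis or renal transplant and lost follow-up" as outcomes, and the treatment section also records deaths.

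No section defines the analysis set, a missing-data method, a rule for a patient without a 12-month value, or a sensitivity analysis. Primary endpoints are mentioned but never listed. I take nPCR as the main outcome because the trial is sized on it.

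**The concern.** A patient who leaves PD follow-up part-way through the year is treated differently depending on which section the analyst follows. Under one reading the patient is absent from the main test. Under another, the patient enters with an early value that reflects only part of any effect. Under a third, the patient appears in some visit-wise tests and not in others.

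At the planned 70 per group, 20% dropout is 14 patients per arm. The exits the plan names (death, hemodialysis transfer, transplant, loss to follow-up) are plausibly linked to nutritional state, so nPCR may well differ between those who stay and those who leave. At stake are the size of the main estimate and the freedom to choose between analyses once the data are known.

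The stated methods do not repair this. The Statistical Methods section assigns analysis of covariance to categorical variables, so no baseline adjustment of nPCR is planned. The regression it describes has PCR as the independent variable, so it is not a group comparison of nPCR.

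**Working it through.** **Inputs from the documents.** SD 0.154 (pilot of 10 patients), target difference δ = 0.090, 50 per group before dropout, 60 after, 70 to be enrolled, 20% dropout overall, visits every 3 months for 12 months. **Assumed**, because the documents are silent: dropout by arm, how it relates to nPCR, when it occurs, and any trend in the control group.

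**1. The plan's own figure.** N = 2[(zα + zβ)σ/δ]² with one-sided 5% and 90% power gives 2 × [(1.645 + 1.282) × 0.154/0.090]² ≈ 50.15, which matches 50. Two-sided 5% gives 46 at 80% power and 53 at 85%. Power and sidedness are not stated, so the match rests on an assumed variant. The 60 is 50 × 1.2. With 70 enrolled and 20% lost, 56 remain per group, with 87.1% two-sided power. The issue is therefore mainly bias, not lost power.

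**2. The wordings applied to one patient whose last visit is month 3.**

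| Wording | What happens to the patient |
|---|---|
| After 12 months | no 12-month value, not in the test |
| Last, meaning the month-12 visit | same as above |
| Last, meaning last available value | enters with the month-3 change |
| Every time point | in the month-3 test only |

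**3. Raw 12-month completer comparison.** Let d be the share who leave and g how far their 12-month values would lie below those of completers, in SDs (T = WeChat, C = control). Then bias = σ(dT·gT − dC·gC).

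- 10% vs 30%, g = 0 in both arms: bias 0.
- 10% vs 30%, g = 0.5 in both: 0.154 × (0.05 − 0.15) = −0.0154, or −17% of 0.090.
- 10% vs 30%, g = 1 in both: 0.154 × (0.10 − 0.30) = −0.0308, or −34%.
- 20% in each arm, same g in both: bias 0.
- 20% in each arm, g = 0.5 in the WeChat arm only: 0.154 × 0.10 = +0.0154, or +17%.

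**4. Last-value change.** Suppose the effect builds linearly, leavers are last seen at fraction f of the year, leaving is unrelated to nPCR, and control drifts by c over 12 months. Then estimate = (c + δ)[1 − dT(1 − f)] − c[1 − dC(1 − f)].

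| Dropout T vs C | c | f = 0.25 | f = 0.75 |
|---|---|---|---|
| 20% vs 20% | 0 | 0.090 × 0.85 = 0.0765 (−15%) | 0.090 × 0.95 = 0.0855 (−5%) |
| 10% vs 30% | 0 | 0.090 × 0.925 = 0.0833 (−7.5%) | 0.090 × 0.975 = 0.0878 (−2.5%) |
| 30% vs 10% | 0 | 0.090 × 0.775 = 0.0698 (−22.5%) | 0.090 × 0.925 = 0.0833 (−7.5%) |

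With c = +0.05, 10% vs 30% and f = 0.25, the estimate is 0.14 × 0.925 − 0.05 × 0.775 = 0.0908, less than 1% off.

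**5. Simulation with leaving related to nPCR.** Settings: 70 per arm, SD 0.154, within-patient correlation 0.4 or 0.6, effect rising linearly to 0.090, 1500 trials per scenario.

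| Dropout scenario | Raw 12-month completers | Last-value change |
|---|---|---|
| Control 29–35%, WeChat 11–14%, likelier after a low nPCR | 0.071–0.084 | 0.087–0.096 |
| Similar in both arms, 18–24% | 0.086–0.089 | 0.078–0.081 |

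A likelihood estimate using all visits gave 0.088–0.090 throughout. Across a wider set of scenarios at about 20% overall dropout, raw completers ranged from about 0.068 to 0.091 (24% too small to 1% too large). Last-value change ranged from about 0.076 to 0.098 (16% too small to 9% too large). Last value can overshoot because it freezes low final values in the arm that loses more patients.

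**The case against.** The strongest reply is that there is no real conflict. Follow-up is fixed at 12 months, so the last measurement is most naturally the month-12 visit, which agrees with SAP item 2. That reading is fair, and the documents nowhere prescribe carrying values forward. It removes the conflict in time point, but it leaves an available-case comparison with no rule for the patients expected to be missing.

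A reader might go further than the documents allow in four ways.

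- *That both analyses are biased whenever dropout differs by arm.* Unequal dropout alone leaves completers unbiased (step 3, g = 0), and equal dropout can still bias last value (step 4).
- *That the two analyses err in opposite directions.* This depends on the scenario. With dropout of about 27% vs 18% and moderate dependence on nPCR, a rerun gave 0.085–0.086 for completers and 0.082–0.084 for last value, both too small.
- *That the plan predicts unequal dropout.* It gives 20% overall and only hopes that hemodialysis transfer and mortality may be lower with WeChat, without a size. Every by-arm rate above is assumed.
- *That any completer analysis is far off.* The larger completer biases belong to raw 12-month values. Completers analysed as change from baseline gave 0.091–0.094 in large-gap, nPCR-dependent runs. But Statistical Methods describes comparing values, so change is not clearly the planned test.

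It is also true that the likelihood model did well partly by construction, since simulated dropout depended only on observed nPCR. Hence the call for a missing-not-at-random check.

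**Conclusion.** The point holds as an undefined main comparison with a better method readily available. It is not a proven bias of known direction. The plan leaves open whether the nPCR effect is measured at 12 months, at each patient's last value or at every visit, and its stated tests discard or misplace information from leavers. Under the assumed scenarios, the simulated error runs from none to about a quarter of the 0.090 target for raw completers, and from 16% too small to 9% too large for last-value change. The simple formulas reach −34% in their most extreme completer case. These figures assume a linear build-up of effect, the pilot SD and invented by-arm dropout. They show that the choice matters, not what this trial would find. The change should be made, since it is cheap and closes off a choice between analyses after the results are seen.

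**What to change.** - State one primary estimand, the between-group difference in nPCR at 12 months, and use it in place of the last-evaluation and last-measurement wording.
- Analyse all enrolled patients in their assigned group. First reconcile Number of study or comparison groups (allocation by patients' willingness) with Specific details of Treatment/Intervention (random allocation).
- Fit a repeated-measures mixed model to the 3-, 6-, 9- and 12-month values with baseline nPCR, group, visit and group-by-visit, and take the 12-month contrast. The data are already planned, "with the patients returning every 3 months for measurement of parameters".
- State how death, hemodialysis transfer and transplant enter the estimand, for example as the nPCR comparison while alive and on PD, with these events reported by arm. A mixed model alone would otherwise imply nPCR values after those events.
- Report dropout by reason and arm. Add a completer analysis and a missing-not-at-random analysis as sensitivity checks.

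The cost is SAP wording and slightly more analysis work, with no added visits. The downside is that the model assumes dropout depends on observed values, which the sensitivity checks are there to probe.
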